14.2 Sample Size/Accrual Rate

A sample size of 34 patients will be accrued and will be required to account for possible drop-out and inevaluability. The early stopping rule is defined above. Anticipated accrual is 1 patient per institution every 2 months. Therefore, accrual is anticipated to take from 20 to 36 months.

14.3 Stratification Factors

- Patients will be analyzed based on the indolent or aggressive type of NHL given that the two groups historically have different outcomes after AutoSCT.
- Patients will be analyzed based on average daily dose of Zydelig through the treatment duration to assess for dose dependence on progression rate.

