3. Patients without evidence of documented disease progression clinically or radiographically (stable disease [SD], partial remission [PR] or complete remission [CR]) who have had count recovery (ANC > 500 cells/mm³, non-transfused platelet count > 20,000 K/mm³) and are at least 30 days post ASCT, but no more than 120 days post ASCT.

Exclusion Criteria:

1. Lack of engraftment
2. Patients with active lymphoma CNS disease

3. Patients with active infection defined as requiring systemic antibiotic treatment and fever within 48 hours of screening.
4. Patients with progressive disease, as defined in protocol section 8.4
5. Patients who progressed while previously taking Zydelig
6. Patients with moderate to severe lung disease including:
 - 6.1. Patients requiring O2 supplementation
 - 6.2. Patients unable to walk 50 feet without stopping to rest
 - 6.3. Moderate to severe obstructive or restrictive disease of the lung
7. Patients with inflammatory bowel disease
8. Patients with active hepatic disease, liver cirrhosis, or known HBV/HCV infection
9. Patients with de novo diffuse large B-cell lymphoma
10. Patients with h/o PCP or CMV infections

Intervention and Mode of Delivery:

Oral Zydelig at 150 mg twice daily continuously on 28-day cycles.

Dose delays/modifications as below for Grade 2 or above for some hematological and non-hematological toxicities such hepatotoxicity, diarrhea/colitis/intestinal perforation, pneumonitis, infections, neutropenia and thrombocytopenia, or any other grade 3 non-hematologic toxicity considered at least possibly related to Zydelig.

Duration of Intervention and Evaluation:

iNHL and tiNHL patients will be eligible after ASCT.

Start of therapy would occur after engraftment, minimum at day 30 post ASCT and no later than 120 days post-ASCT.

Patients will continue on Zydelig up to one year or to progression/relapse/death or unacceptable toxicity, whichever occurs first.

HDT/ASCT will occur as soon as possible based on successful mobilization, collection and infusion of bone marrow or peripheral blood stem cells at a minimum of 2×10^6 CD34+/Kg of weight.

Myeloablative transplant preparative regimen is based on institutional standards.

Engraftment will be defined as ANC over 500 cells/mm³ and non-transfused platelet count of 20K/mm³. Standard supportive care in the post-transplant setting will be given.

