5. TREATMENT PLAN

5.1 Zydelig Administration

Treatment will be orally administered on an inpatient and outpatient basis with the starting dose of 150 mg by mouth twice a day for continuous 28-day cycles. Treatment will continue until progression, intolerance, or patient/physician discretion to stop therapy. Zydelig will be started with count recovery (ANC over 500 cells/mm³, non-transfused platelet count over 20,000 K/mm³) in patients who are at least 30 days after induction and/or transplant but no more than 120 days post-transplant.

Reported adverse events and potential risks are described in Section 9. Appropriate dose modifications for Zydelig are described in Section 7. No investigational or commercial agents, or therapies other than those described below may be administered with the intent to treat the patient's malignancy.

Patients should swallow Zydelig tablets whole each morning and evening (i.e. every 12 hours). Tablets may be taken with or without food. Patients should keep track of adherence to Zydelig therapy by using the "Patients Drug Diary" (see appendix B). This diary will be collected at the end of each cycle. At the time of collection, the diary will be reviewed by a staff member and the patient will be prompted to complete any blank entries before completion of the visit. Should a patient miss or vomit a dose of Zydelig within less than 6 hours of the planned dose, the patient should take it as soon as possible. Patients who miss or vomit a dose of Zydelig longer than 6 hours after the planned dose should wait until the next scheduled dose to resume taking Zydelig.

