5.3 Duration of Therapy

In the absence of treatment delays due to adverse events, treatment may continue for 1 year or 12 cycles (28 days per cycle) after transplant or until one of the following criteria applies:

- Disease Progression
- Intercurrent illness that prevents further administration of treatment
- Unacceptable adverse event(s)
- Evidence of PCP pneumonia or CMV viremia, confirmed at 2 consecutive blood draws at least 1 day apart with any value ≥ 500 IU/mL in plasma or evidence of documented CMV disease.
- Patient decides to withdraw from the study
- General or specific changes in the patient's condition render the patient unacceptable for further treatment in the judgment of the investigator.

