7. DOSING DELAYS/DOSE MODIFICATIONS

Please refer to table 2 below.

Patients who experience a Grade 2 or 3 toxicity and recover to \leq Grade 1 (or to pretreatment baseline level of toxicity) may continue treatment at the next lower dose level (i.e., Dose level 2 down to dose level 1).

Once the dose has been reduced, patients must remain at the reduced dose for 28 days. Dose escalation may occur at the discretion of the investigator and may occur every 28 days. Patients may have their dose de-escalated from level 2 to level 1, three times before being removed from treatment.

Please note:

- There are no dose escalations above 150 mg BID
- There are no dose reductions below 100 mg BID

Table 2

Dose Modification Schedule	
Dose Level	Dose of Zydelig
Level 2 (starting dose)	150 mg PO BID
Level 1	100 mg PO BID

Table 3

Dose Modifications for Toxicities Due to Zydelig

Pneumonitis	Any symptomatic pneumonitis		
	Discontinue Zydelig in patients with any severity of symptomatic pneumonitis		
ALT/AST	>3.0-5.0 x ULN	>5-20 x ULN	>20 x ULN
	Decrease Zydelig to 100 mg BID and monitor weekly until ≤ 1 x ULN.	Withhold Zydelig. Monitor at least weekly until ALT/AST are ≤ 1 x ULN, then may resume Zydelig at 100 mg BID.	Discontinue Zydelig permanently.
Bilirubin	>1.5-3 x ULN	>3-10 x ULN	>10 x ULN

	Decrease Zydelig to 100 mg BID. Monitor at least weekly until ≤ 1 x ULN.	Withhold Zydelig. Monitor at least weekly until bilirubin is ≤ 1 x ULN, then may resume Zydelig at 100 mg BID.	Discontinue Zydelig permanently.
Diarrhea*	Moderate diarrhea	Severe diarrhea or hospitalization	Life-threatening diarrhea
	Decrease Zydelig to 100 mg BID. Monitor at least weekly until resolved.	Withhold Zydelig. Monitor at least weekly until resolved, then may resume Zydelig at 100 mg BID.	Discontinue Zydelig permanently.
Neutropenia[^]	ANC 1.0 to <1.5 Gi/L	ANC 0.5 to <1.0 Gi/L	ANC <0.5 Gi/L
	Maintain Zydelig dose.	Decrease Zydelig to 100 mg BID. Monitor ANC at least weekly.	Interrupt Zydelig. Monitor ANC at least weekly until ANC ≥ 0.5 Gi/L, then may resume Zydelig at 100 mg BID.
Thrombocytopenia	Platelets 50 to <75 Gi/L	Platelets 25 to <50 Gi/L	Platelets <25 Gi/L
	Maintain Zydelig dose.	Decrease Zydelig to 100 mg BID Monitor platelet counts at least weekly.	Interrupt Zydelig. Monitor platelet count at least weekly. May resume Zydelig at 100 mg BID when platelets ≥ 25 Gi/L.

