7.1 Other Non-hematologic Toxicity

For other grade 3 non-hematologic toxicity considered at least possibly related to Zydelig, interrupt Zydelig until toxicity improves to \leq grade 2, and then resume Zydelig with one dose level reduction for all subsequent cycles.

For other grade 4 non-hematologic toxicity, discontinue Zydelig.

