8. CRITERIA FOR RESPONSE, PROGRESSION, AND RELAPSE

For purposes of this study, patients should be restaged every 3 cycles during treatment (i.e., cycles 3, 6, 9, 12, etc.), then every 3 months for 1 year, then every 6 months for another year.

The Revised Response Criteria for Malignant Lymphoma is adopted.¹³

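### Section 14.3 averages dose over a treatment period that progression itself can end, so the exploratory dose-progression estimate can be biased even if dose has no effect (minor)

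*Combined protocol and SAP*

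**What the plan says.** The second bullet of 14.3 defines the exposure and its purpose: "Patients will be analyzed based on average daily dose of Zydelig through the treatment duration to assess for dose dependence on progression rate". It names no model, landmark or fixed window.

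Three places make progression an end of treatment. The Synopsis says "Patients will continue on Zydelig up to one year or to progression/relapse/death or unacceptable toxicity, whichever occurs first". Section 5.1 says "Treatment will continue until progression, intolerance, or patient/physician discretion to stop therapy". Section 5.3 says "treatment may continue for 1 year or 12 cycles (28 days per cycle) after transplant or until one of the following criteria applies", and disease progression heads the list that follows.

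Dose can move both ways. Section 7 has two levels, 150 mg and 100 mg twice daily, and says of the way back up: "Dose escalation may occur at the discretion of the investigator and may occur every 28 days". For other grade 3 non-hematologic toxicity, 7.1 instead says "resume Zydelig with one dose level reduction for all subsequent cycles".

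PFS is counted from ASCT (14.4.1), but the first dose comes later: "Start of therapy would occur after engraftment, minimum at day 30 post ASCT and no later than 120 days post-ASCT". Section 14.4.4 names Cox regression for PFS and OS risk factors and does not mention time-dependent dose. Its reference to suitable statistical models concerns the correlative findings, not dose.

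The Synopsis, 5.1 and Table 2 give a starting dose of 150 mg twice daily. Section 14.1 gives the first dose as 100/150 mg twice daily, Section 4 speaks of confirming a dose assignment, and the Appendix B diary has a field for a dose cohort. These passages must be reconciled.

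**The concern.** An exposure measured after baseline should not depend on the outcome it is meant to explain. Here it does. A patient who progresses at week 8 is averaged over eight weeks, and one who does not progress may be averaged over 12 cycles. If doses mostly fall over time, the short window gives the higher average and a higher dose looks worse. If doses fall early and are then restored, the short window gives the lower average and a higher dose looks better. Either pattern can appear with no dose effect, and either can hide a real one.

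Readers may use this result to judge whether a reduced dose costs disease control. That is what is at stake. The analysis is not a listed objective, and the primary endpoint and sample size do not depend on it.

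**Working it through.** **Plan's own figure.** The plan gives none for this analysis, so there is nothing to reproduce.

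**Inputs from the documents.** 300 mg/day at full dose and 200 mg/day when reduced (Section 7); up to 12 × 28 = 336 days on drug (5.3); first dose on days 30-120 after ASCT (Synopsis); restaging every 3 cycles, that is 84 days (Section 8); follow-up for 24 months after treatment (5.4); 1-year PFS of 60% or 80% (1.2.1); n = 34.

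**Assumptions.** 50% of patients reduced by day 336; 30% removed for toxicity (Section 14 treats this rate as acceptable); constant progression hazard; early reductions fall on days 7-84; re-escalation comes 28-84 days after reduction.

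**Step 1: reductions spread evenly, none reversed.** The reduction hazard is λ = ln 2/336 = 0.00206 per day. If treatment ends on day e, the expected average dose is

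200 + 100 × (1 − exp(−λe))/(λe) mg/day.

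- e = 28: 297
- e = 84: 292
- e = 168: 285
- e = 336: 272

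The gap between stopping at day 28 and at day 336 is 25 mg/day, with no dose effect.

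**Step 2: the opposite direction.** Take a patient reduced on day 28 and restored on day 84. If treatment ends on day 84, the average is (28 × 300 + 56 × 200)/84 = 233 mg/day. If it ends on day 336, the average is (28 × 300 + 56 × 200 + 252 × 300)/336 = 283 mg/day. The short window now gives the lower average.

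**Step 3: simulation with no dose effect.** Cox model on the whole-treatment average, ASCT clock, patients entering the risk set at first dose. The table gives the large-sample hazard ratio per +50 mg/day (truth 1.00). Ranges cover both PFS values and repeated runs.

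| Reductions | No restaging or removal, follow-up to day 730 after ASCT | Restaging, 30% removal, 24 months after treatment |
|---|---|---|
| Even, none reversed | about 1.4-1.5 | 1.14-1.21 |
| Early, none reversed | 1.20-1.25 | 1.02-1.09 |
| Early, half reversed | 1.05-1.13 | 1.01-1.03 |
| Early, all reversed | 0.30-0.42 | not calculated |

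The last row is a bound only, because 7.1 rules out reversal for some toxicities. The right-hand column follows the protocol more closely. The bias shrinks there partly because longer follow-up adds progressions off drug, which do not set the averaging window.

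**Step 4: precision.** Full treatment plus 24 months is 336 + 730 = 1,066 days. Events are then 34 × (1 − 0.60^(1066/365)) = 26 or 34 × (1 − 0.80^(1066/365)) = 16. Removal shortens some follow-up, and the simulation gives about 15-26. Stopping at day 730 after ASCT gives 11-20.

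**Step 5: the time-updated average.** Dose averaged from first dose up to each event time, with time counted from first dose, gave hazard ratios near 1 (0.99-1.05 with held days as 0 mg). At n = 34, false positives were 4-8% against a two-sided 5% yardstick, and the sign split was 48-54%. On the ASCT clock with delayed entry and restaging the sign split drifted to 44-54%, because "patients should be restaged every 3 cycles during treatment" ties assessments to treatment time. A day-84 landmark also worked in a separate set of 24 null scenarios: 0.94-1.03 per +100 mg/day. Dividing by a fixed 336 days is no remedy, since it reversed the bias (0.00-0.54 per +100 mg/day).

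**The case against.** The best defence is that this is one exploratory line in a 34-patient study, with no model or test attached, and that the bias may be small. Much of that stands. With half the reductions reversed, and with restaging and removal included, the estimate is close to 1. At n = 34 and 50% reduced, evenly spread and not reversed, with restaging and removal but follow-up to day 730, false positives were only 5.0-6.8% against 5%. The plan sets no test level for dose, so no error rate of its own is breached.

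A reader might infer a hazard ratio near 1.5, or false positives up to 26%. The documents do not support that size. Such figures need runs without scheduled restaging, without removal for toxicity and with follow-up cut at day 730. The 26% also needs 70% of patients reduced. Section 8 schedules restaging, Section 14 plans around removal for toxicity, and 5.4 sets longer follow-up.

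It does not stand that the analyst will handle this anyway. Section 14.3 defines the exposure explicitly as the whole-treatment average, and no other section corrects it.

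**Conclusion.** The concern holds as a minor, exploratory point: followed as written, the second bullet of 14.3 can give a biased estimate when dose has no effect. On the protocol's restaging and follow-up, with the assumed 50% reduced and 30% removed, the null hazard ratio per +50 mg/day is about 1.1-1.2 for evenly spread, unreversed reductions. It is about 1.0-1.1 if reductions are early or half are reversed.

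A reader might also infer that the bias always makes a higher dose look worse. The documents do not settle the direction. They give neither the timing of reductions nor the share reversed, and in runs with early reductions the sign turned near 75% reversed. The 100/150 mg wording in 14.1 adds uncertainty, because all runs start every patient at 300 mg/day. Nothing here affects the primary toxicity decision.

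**What to change.** Replace the second bullet of 14.3 with:

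> Exploratory and descriptive: the association of dose with progression will be assessed in a Cox model with dose as a time-dependent covariate, defined as the average daily dose from first dose up to each event time (or to end of treatment if earlier), counting held days as 0 mg. Time is measured from first dose. Death without progression is censored in this cause-specific model; PFS is reported as a supporting outcome. The estimate is reported with a 90% confidence interval.

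This keeps progression as the outcome, as 14.3 does, and uses the interval level of 14.4.1. A landmark analysis is an acceptable alternative. Separately, reconcile the starting-dose wording in 14.1, Section 4 and Appendix B with the Synopsis, 5.1 and Table 2.

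The cost is one bullet and slightly more analysis work; the dose diaries (5.1, Appendix B) already supply the data. Four limits remain:

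- Precision is low with 34 patients.
- The average is frozen at end of treatment, so patients removed early can keep a high average and a real dose effect may be blurred.
- Dose stays confounded with toxicity and prognosis.
- The result therefore cannot be read as a causal dose effect.

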14.4 Analysis of Secondary Endpoints

14.4.1 1-year PFS after ASCT.

PFS is defined as the time from the date of ASCT till progression or death whatever comes first. PFS function will be estimated using the Kaplan-Meier approach with 90% Confidence Interval.

Analysis of secondary objective(s):

The 1-year PFS will be estimated and reported using the Kaplan-Meier curve with the corresponding 90% confidence interval.

- 14.4.2 2-year PFS will be calculated with the same method as 1-year PFS (see 13.4.1).
- 14.4.3 Cumulative incidences of NRM at 3 months and 12 months by competing risks model and Grey's test.
- 14.4.4 The Cox regression model will be used to assess plausible risk factors for PFS and OS. The correlatives findings will be incorporated into time-to-event analyses using appropriate statistical models. Statistical analysis will be conducted by the BSS of the GCC.
- 14.4.5 Correlatives Studies
Please see Appendix C

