Zydelig (Idelalisib) is the 1st marketed PI3K δ inhibitor that has been effective against indolent B-cell lymphomas (iNHL) with remarkable activity in heavily treated patients, leading to an overall response rate (ORR) of 57%, a median progression free survival (PFS) of 11 months and a median duration of response of 12.4 months.¹

We propose to incorporate Zydelig into a maintenance paradigm post ASCT for patients with iNHL and transformed iNHL (tiNHL). The goal of this strategy is to increase the likelihood that patients are able to maintain a remission after ASCT at 1 and 2 years of follow-up.

Mirroring the paradigm incorporating BCR/ABL TKI, lenalidomide and Sorafenib therapies in the post-transplant treatments of Ph+ ALL, MM, and FLT3 ITD AML respectively, we propose inhibiting the proliferation and survival of iNHL cells by blocking the B-cell receptor signaling (BCR) via inhibiting the downstream molecular target PI3K δ with Zydelig in the post-transplant setting.

[figure not shown]
Primary Objective(s):

1. Determine the toxicity and safety of incorporating Zydelig into the post- ASCT maintenance setting for iNHL and tiNHL immediately after ASCT.

Secondary Objective(s):

1. Assess the efficacy of incorporating Zydelig into the post-ASCT maintenance setting for iNHL and tiNHL immediately after ASCT with a corresponding endpoint of 1-year PFS after the transplantation.
2. 2-year Progression Free Survival (PFS).
3. Non-relapse mortality (NRM).
4. Overall survival (OS).
5. Correlatives studies:
 - a. To perform pharmacodynamics studies.
 - b. To understand mechanism of resistance to Zydelig.
 - c. To assess the effect of Zydelig on the immune system.

Study Design:

Number of Patients:

We will be studying a cohort of 34 patients with iNHL or tiNHL.

Main Criteria for Inclusion/Exclusion:

Inclusion Criteria - must meet all

1. iNHL as defined by follicular lymphoma (FL), marginal zone lymphoma (MZL), lymphoplasmacytic lymphoma/Waldenstrom disease (LPL/WM) and small lymphocytic lymphoma (SLL) or tiNHL as defined by large B cell transformation of any of the above entity.
2. Patients must be eligible to undergo high dose chemotherapy (HDT) followed by ASCT as a form of remission consolidation.

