1.2. Secondary Objectives

1.2.1. Assess the efficacy of Zydelig into the post- ASCT maintenance setting for iNHL and tiNHL immediately after ASCT.

The corresponding endpoint is to report the 1-year PFS after the transplantation. PFS is defined as time to progression, relapse of the disease or death. The efficacy endpoint would be improvement of 1-year PFS after ASCT by 20% based on an approximate baseline PFS of 60% for iNHL and tiNHL.^{1,2} The expected 1-year PFS will be around 80%.

Survival without progression or death will be determined using the Kaplan-Meier estimates at 1 year post ASCT.

1.2.2. 2-year PFS.

2-year PFS will be determined using the Kaplan-Meier estimates at 2 years post ASCT.

1.2.3. Non-relapse mortality (NRM).

NRM is defined as death in the absence of competing risks, relapse or progression of disease. This secondary endpoint will be characterized and presented as a cumulative incidence at 3 months and 12 months after SCT.

1.2.4. Overall survival (OS).

Survival without death will be determined and presented as Kaplan-Meier estimates at 1 and 2 years post ASCT.

1.2.5. Correlative studies.

See Appendix D.

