3. PATIENT SELECTION

3.1. Eligibility Criteria

3.1.1. Inclusion Criteria (must meet all)

1. Histologically documented (by HPI or pathology report) iNHL as defined by follicular lymphoma (FL), marginal zone lymphoma (MZL), lymphoplasmacytic lymphoma/Waldenstrom disease (LPL/WM) and small lymphocytic lymphoma (SLL) or tiNHL as defined by large B cell transformation of any of the above entities including chronic lymphocytic leukemia (CLL)
2. Patients must be eligible to undergo high dose chemotherapy (HDT) followed by ASCT as a form of remission consolidation
3. Patients without evidence of documented disease progression clinically or radiographically after ASCT (stable disease (SD), partial remission (PR) or complete remission (CR)) who have had count recovery (ANC > 500 cells/mm³, non-transfused platelet count > 20,000 K/mm³) and are at least 30 days post ASCT but no more than 120 days post ASCT

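### PFS, OS and NRM are timed from transplant although patients enter only at day 30 to 120 without progression, so the planned estimates contain guaranteed event-free time

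*Combined protocol and SAP*

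**What the plan says.** **Clock.** Section 14.4.1: "PFS is defined as the time from the date of ASCT till progression or death whatever comes first". The synopsis states its first secondary objective "with a corresponding endpoint of 1-year PFS after the transplantation". Only section 1.2 gives the origin for the other two endpoints. NRM is to be "characterized and presented as a cumulative incidence at 3 months and 12 months after SCT" (1.2.3). For OS, "Survival without death will be determined and presented as Kaplan-Meier estimates at 1 and 2 years post ASCT" (1.2.4).

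**Entry.** Section 3.1.1 requires stable disease or better after transplant, recovered counts, and a patient who is "at least 30 days post ASCT but no more than 120 days post ASCT". The synopsis repeats the window for treatment: "Start of therapy would occur after engraftment, minimum at day 30 post ASCT and no later than 120 days post-ASCT".

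**Method.** "PFS function will be estimated using the Kaplan-Meier approach with 90% Confidence Interval" (14.4.1). NRM uses a competing-risks model (14.4.3), and Cox regression is named for PFS and OS (14.4.4). Delayed entry, left truncation, a landmark, or an origin at registration or first dose appears nowhere.

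**Yardstick.** Section 1.2.1 frames efficacy as "improvement of 1-year PFS after ASCT by 20% based on an approximate baseline PFS of 60% for iNHL and tiNHL" and expects about 80%.

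**The concern.** A patient who progresses or dies before entry is never enrolled. If every enrolled patient is counted at risk from day 0, the first 30 to 120 days are event-free by design, which is 8% to 33% of the 1-year window (30/365 to 120/365). The resulting curve describes patients who reached entry without an event. The plan nevertheless calls it PFS after transplant and sets it against a 60% baseline also described as after transplant.

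The section 1.2.1 comparison is at stake. If the 60% refers to everyone transplanted, part of any apparent gain comes from the entry window and would appear with an inactive drug. OS is inflated and NRM deflated in the same way, though the documents give no benchmark for either. The 3-month NRM is the extreme case, since a patient entering after day 90 cannot contribute an event to it.

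**Working it through.** **Plan's own figures.** Section 14 gives no power or precision for PFS, OS or NRM, so there is nothing of that kind to reproduce. Its Type I error of 0.075 and power of about 80% concern the toxicity endpoint. They reproduce with 31 patients and success at 20 or more (0.0748 and 80.8%) and do not involve the survival clock.

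**Inputs.** From the documents: 1-year PFS 60% and target 80% (1.2.1), entry at days 30 to 120 (3.1.1), 34 patients (14). Assumed, because the documents are silent: the 60% runs from transplant in all transplanted patients; no drug effect; Weibull hazard with shape *k* from 0.7 to 1.3; entry uniform over the window unless stated; no censoring before 1 year.

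**Step 1: what the planned estimator targets.** Let S(t) = exp[ln(0.6)·(t/365)^k]. For a patient entering event-free on day *e*, the chance of being event-free at 1 year is S(365)/S(e). With constant hazard (*k* = 1):

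- day 30: S(30) = 0.6^(30/365) = 0.959, and 0.60/0.959 = 0.626
- day 120: S(120) = 0.6^(120/365) = 0.845, and 0.60/0.845 = 0.710

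| Shape | All enter day 30 | Uniform 30–120 | All enter day 120 |
|---|---|---|---|
| 0.7 | 65.6% | 70.9% | 75.8% |
| 1.0 | 62.6% | 66.7% | 71.0% |
| 1.3 | 61.2% | 64.2% | 67.7% |

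The artefact is about 1 to 16 points. In the central case it is 6.7 points, and 6.7/20 is about one third of the hoped-for gain. At 2 years (*k* = 1, uniform entry) the estimate targets 40.0% against a true 0.6² = 36.0%.

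**Step 2: effect in trials of 34 with no drug effect.** Uniform entry, 200,000 simulated trials; the unbiased column is exact Binomial(34, 0.6).

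| Event | Planned estimate, k = 1 | Unbiased |
|---|---|---|
| Point estimate above 60% | 79% | 49% |
| Lower 90% limit above 60%, plain | 26% | 7% |
| Lower 90% limit above 60%, log-log | 15% | 3% |
| Point estimate 80% or more | 3% | 0.5% |

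Over shapes 0.7 to 1.3 the planned-estimate figures are 69–91% for the first row, 17–45% for the second and 2–10% for the last. The plan contains none of these as a decision rule; they only show how the result would tend to look.

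**Step 3: 3-month NRM.** With uniform entry the share entering after day 90 is (120 − 90)/90 = 1/3. Mean time at risk before day 90 is the average of max(0, 90 − e), that is (60²/2)/90 = 20 days, or 22% of the 90. This step uses no hazard model and no benchmark.

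**Step 4: do the remedies work?** With *k* = 1, timing from first dose recovers 0.600 in large samples. Delayed-entry Kaplan-Meier gives 0.626, matching S(365)/S(30). At n = 34 the delayed-entry estimate has SD about 0.10, against about 0.08 for the planned or first-dose estimate, and it collapsed to zero in 0.3% of 20,000 runs because few patients are at risk near day 30.

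**The case against.** Kaplan-Meier from transplant is a correct description of the enrolled cohort, and the protocol's aim is confined to the maintenance setting. On that view the defect is a missing label and an unmatched benchmark. The studies behind the 60% are not described; if they already excluded early failures, the PFS gap shrinks. The endpoint is secondary and untested. The 6.7-point artefact is about half the 90% half-width at this sample size (1.645·√(0.24/34) = 13.8 points), and selection alone seldom reaches 80%. The 16-point extreme needs every patient to enter at day 120 with a falling hazard. First-dose timing does not remove dependence on the unknown hazard either: its matched benchmark runs from 0.56 to 0.66 over the same shapes, against 0.64 to 0.71 for a benchmark matched to the transplant clock. Delayed-entry methods also require entry day to be unrelated to prognosis, which is doubtful when entry depends on count recovery.

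Much of this stands as a limit on size and on the choice of remedy. It does not remove the problem. The plan gives no conditional label and itself sets the estimate against a 60% after-transplant figure. The direction of the error is certain whenever events occur in the excluded window, and the NRM point needs no benchmark at all.

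**Conclusion.** The concern holds. Followed as written, section 14.4 gives PFS and OS that are too high and NRM that is too low as statements about outcome after transplant. Confidence is high on the design facts and the direction. The size is an illustration: it rests on the unstated entry-day distribution, the early hazard, and the 60% being unconditional from transplant. The harm is to interpretation of the stated efficacy aim, and it should be fixed before analysis. The toxicity endpoint, the 34 patients and the stated error rates do not depend on it.

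**What to change.** **Preferred.** In the synopsis objectives, sections 1.2.1 to 1.2.4 and section 14.4, time PFS, OS and NRM from the first dose of Zydelig. Compare 1-year PFS with a benchmark measured from the same landmark in patients progression-free at that point. If 60% holds from transplant and entry is uniform, that benchmark is 0.60 under constant hazard, 0.66 at shape 0.7 and 0.56 at shape 1.3. This clock also fits the schedule, since baseline imaging and restaging are tied to treatment (sections 6 and 8).

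**If the transplant origin is kept.** Use delayed-entry Kaplan-Meier and Aalen-Johansen estimates, with each patient joining the risk set at first dose. Label them conditional on being event-free at about day 30, and compare with S(365)/S(30): 0.63 under constant hazard, 0.61 to 0.66 over shapes 1.3 to 0.7. State the assumption that entry day is independent of prognosis. A lighter version keeps ordinary Kaplan-Meier, labels it conditional on entry, and averages S(365)/S(entry) over the observed entry days as the benchmark. Benchmarks for the transplant clock must not be applied to first-dose timing.

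**In either case.** State whether the source of the 60% was restricted to patients progression-free after transplant. Drop the 3-month NRM after transplant or count it from first dose.

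**Cost.** Wording, plus the delayed-entry option in the analysis code if that route is taken. The apparent gain will probably be smaller, survival from day 0 cannot be recovered, first-dose results are not directly comparable with published figures from transplant, and the delayed-entry estimate is less precise.
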